## 3.3 Study Duration and Periods

The total time of active participation in the study (including screening, treatment and wash-out periods) is 2.25 years for each subject completing the study (see Schedule of Activities; Sec. 7.7), and includes:

- Screening of up to 60 days from Screening Visit 1 (SC1) to enrollment at Baseline Visit. Because of the substantial (~50%) chance that the results of serum urate screening test will be exclusionary (Fig. 9, Sec. 3.1), the screening process at PSG sites is split into two visits with testing on a brief initial visit (SC1) primarily limited to the serum urate measurement. For those subjects who pass SC1, most of the remaining screening procedures are conducted on a longer second screening visit (SC2) and if still eligible then a subsequent DAT brain scan at a local neuroimaging center.
- Treatment (Period 1) of 720 ± 7 days (~24 months) approximates the 2-year observation periods of the DATATOP, PRECEPT and SURE-PD studies, on which the present trial is modeled. Extending follow-up beyond 24 months would provide diminishing returns as the primary outcome variable of MDS-UPDRS score is censored from the primary analysis after initiation of symptomatic antiparkinsonian therapy, which is expected to have occurred in the majority (two thirds) of placebo subjects by that point. Randomized, placebo-controlled, double-blind treatment is initiated at the baseline visit (BL) and gradually advanced and titrated up to a maximum 6 capsules/day or until the target serum urate range of 7.1-8.0 mg/dL is reached in the inosine-treated group. After wash-in/titration visits (V01, V02) at 3 and 6 weeks after BL, scheduled visits (V03 V10) will occur at 3-month intervals for clinical and safety assessments, including a serum urate measurement for any algorithmic dosage adjustments needed to maintain levels within the 7.1-8.0 mg/dL target range for those in the inosine group. Mirrored adjustment in the number of placebo capsules/day help ensure subject and site staff remain blind to treatment assignment.

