3.5 Symptomatic Effects

Symptomatic effects will be estimated by changes in motor symptoms (a) during the first 3 months of wash-in at the start of period 1, and (b) during the 3-month wash-out during period 2 or at the end of study drug exposure, if earlier.

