5.15 Blindedness Evaluation

At week 6 and either month 24 (V10), V10-equivalent visit due early study closure, an Unscheduled Visit due to study drug discontinuation, or a Discontinuation of In-person Followup Visit (whichever of the 4 visits comes first), the Site Investigator, Coordinator, and subject will complete a blindedness evaluation in which each is asked to give his/her independent impression of the subject's treatment assignment and the primary and secondary reasons for this opinion. Participants' responses will not be available to the site Investigator or Coordinator when they make their assessments.

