6.6.8 Symptomatic Effects

The presence of symptomatic effects will be tested using a change-point model constructed as a partial linear spline over time with knots at 12 weeks and 24 months. Both fixed and subject-specific random terms for intercept, slope from baseline to 12 weeks, slope from 12 weeks to 24 months, and slope from 24 to 27 months (or from V10-equivalent visit on study drug to SV) will be included. Unstructured covariance will be assumed among the random effects (10 terms). The AT sample will be analyzed. Significantly smaller slopes during wash-out among subjects treated with inosine using one-sided testing at alpha = 0.025 will be interpreted as symptomatic effects. If symptomatic effects are not found on that basis, the absence of symptomatic effects will be judged based on a non-inferiority test using a non-inferiority bound of 6.3 / 3 = 2.1 points/month in the direction of a symptomatic effect and using one-sided testing at alpha = 0.05.

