6.8.6 Placebo Response

The frequency of a placebo-associated improvement in activities of daily living (ADL) and motor symptoms as measured by the MDS-UPDRS Parts IB and II and Part III, respectively, will be summarized among all placebo arm participants, by visit, and by site. Following Goetz et al. 2000, we will define placebo-associated improvement as a reduction in the ADL or motor score of at least 50% or an improvement from baseline of two or more points on at least two different items of the respective MDS-UPDRS scale. Stability of the rates of placebo-associated improvements will be tested across visits using mixed model logistic regression with fixed effects of visit and random participant-specific intercepts. The following predictors of placebo-associated improvement at any visit will be tested by logistic regression:

- age at baseline (less than 65 years versus greater or equal to 65 years),
- disease duration at baseline (less than 2 years vs. greater or equal to 2 years),
- disease severity at baseline (modified Hoehn and Yahr Stages 1 and 1.5 vs. 2 and 2.5),
- number of years education (Q1 on Socio-Economics form)
- daily caffeine intake: lower vs higher (Q3 + 0.3xQ4 from Smoking, Alcohol and Caffeine form)
- expectation of inosine: "A lot better" vs "Somewhat better" vs "No change" or worse (Q2 on PD-Expectancy questionnaire)
- expectation of inosine-placebo difference: >/=2 vs <2 units more favorable for inosine (Q2 - Q1 on PD-Expectancy questionnaire)
- preference for inosine: "strong" vs other (Q3 on PD-Expectancy questionnaire)
- treatment belief: placebo vs inosine (Q2 on Blindedness Questionnaire).

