6.8.7 Blindedness

Descriptive stats will be summarized for responses on the early and late administrations of the Blindedness Questionnaire and the change between them. The following predictors of treatment assignment belief reported on the Blindedness Questionnaire will be tested by logistic regression. For belief of inosine assignment (stratified by correct and incorrect):

- age at baseline (categorized as <65 years vs. ≥ 65 years)
- sex
- treatment assignment
- MDS-UPDRS I-III censored change at wash-in (per 6.6.8) for response at the 6-week (V02) administration
- MDS-UPDRS I-III censored change to \sim 24-mo/V10 for response at the \sim 24-mo/V10 administration
- history of preceding nephro-lithiasis TEAE
- history of preceding gout, gout-like or other arthritic TEAE
- average preceding daily number study drug capsules
- expectation of inosine: "A lot better" vs "Somewhat better" vs "No change" or worse (Q2 on PD-Expectancy questionnaire),
- expectation of inosine-placebo difference: >/=2 vs <2 units more favorable for inosine (Q2 - Q1 on PD-Expectancy questionnaire)
- preference for inosine: "strong" vs other (Q3 on PD-Expectancy questionnaire).

7. References

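### The week-6 treatment-guess model uses a symptom change that runs to week 12, so about half of the predictor window falls after the guess it is meant to predict.

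*SAP*

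**What the plan says.** SAP 6.8.7 tests predictors of treatment belief by logistic regression. One of them is "MDS-UPDRS I-III censored change at wash-in (per 6.6.8) for response at the 6-week (V02) administration". The cross-reference leads to SAP 6.6.8, which fits a "partial linear spline over time with knots at 12 weeks and 24 months" and names its first two segments as "slope from baseline to 12 weeks, slope from 12 weeks to 24 months". SAP 3.5 agrees: symptomatic effects are estimated "during the first 3 months of wash-in at the start of period 1". In the same 6.8.7 list, the nephrolithiasis history, the gout and arthritis history and the capsule count are each restricted to what preceded the guess.

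SAP 6.8.6 takes placebo-arm improvement at any visit as the outcome and lists nine predictors. Eight are baseline items. The ninth is "treatment belief: placebo vs inosine (Q2 on Blindedness Questionnaire"). The questionnaire is given early (week 6) and late, to participants, site investigators and coordinators (SAP 4.7). SAP 6.8.6 does not say which administration or which respondent supplies the predictor.

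**The concern.** A model that explains a week-6 guess should use information that existed by week 6. Here the symptom predictor also takes in the six weeks after the guess. Influence in that direction is plausible: Parts IB and II of the MDS-UPDRS are completed by the participant and Parts IA and III are rated by the Site Investigator (SAP 5.1), and both also record guesses (SAP 4.7). Someone who decides at week 6 that the capsules are inosine may score better at week 12. An association between wash-in change and belief could then mean that perceived change informed the guess, or that the guess coloured later scores, and the model could not tell which.

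The placebo-response model has a related gap. If the administration is left open and improvement counts at any visit, some of the improvement can come before the belief said to predict it.

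**Working it through.** The documents give no figure for either model, so there is nothing to reproduce. The check is one of time order.

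**Week-6 guess (SAP 6.8.7)**

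Inputs: V02 is day 42 ± 5 and V03 is day 84 ± 7 (Protocol 7.2.3, 7.2.4). The predictor window is baseline to week 12 (SAP 6.6.8, 3.5).

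1. Share of the window after the guess = (V03 day − V02 day) / V03 day.
   - Nominal: (84 − 42) / 84 = 50%.
   - Smallest, V02 late and V03 early: (77 − 47) / 77 = 39%.
   - Largest, V02 early and V03 late: (91 − 37) / 91 = 59%.
2. How much the week-12 score matters. As an illustration only, take an ordinary least-squares line through scores at weeks 0, 3, 6 and 12. The mean time is 5.25 weeks and the sum of squared deviations is 27.5625 + 5.0625 + 0.5625 + 45.5625 = 78.75. Each score's weight on the 12-week change is 12 × (t − 5.25) / 78.75.
   - Week 12: 12 × 6.75 / 78.75 = +1.03. Its share of the slope information is 45.5625 / 78.75 = 58%.
   - Week 6: 12 × 0.75 / 78.75 = +0.11. Its share is 0.5625 / 78.75 = 0.7%.

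   In this illustration the score taken after the guess dominates the predictor, and the score from the guess visit counts for little. The SAP model is a mixed-model spline, so its exact weights will differ.
3. With change from baseline to V02 instead, 0% of the window lies after the guess visit.

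**Placebo response (SAP 6.8.6)**

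Inputs: ten scheduled treatment-period visits after baseline, V01 to V10, leaving out the off-drug Month 27 visit.

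| Belief used | Visits before it | Same visit | Visits after it |
|---|---|---|---|
| Week 6 (V02) | 1 (V01) | 1 (V02) | 8 (V03–V10) |
| Late, completed at V10 | 9 (V01–V09) | 1 (V10) | 0 |

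Under either choice, improvement at any visit can come before the belief. Only the week-6 answer leaves treatment-period visits that follow it.

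**The case against.** The best defence of the week-6 item is that wash-in could mean the first six weeks. Protocol 3.3 has the phrase "After wash-in/titration visits (V01, V02) at 3 and 6 weeks after BL". But the SAP item points explicitly to 6.6.8, whose first segment ends at week 12, and the SAP's introduction makes the SAP authoritative on data analysis. What stands is that the predictor is measured partly, not wholly, after the guess.

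A reader might infer more than the documents support:

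- **That the late guess is mis-ordered too.** SAP 5.15 does place the late questionnaire at "whichever of the 4 visits comes first", so some people complete it early. But the 6.8.7 item pairs change to about month 24 with the response at about month 24, which is in order.
- **That few participants can enter the late model.** The planning rates give 1 − 0.70 − 0.08 = 0.22, and 0.22 × 270 = 59. That assumes a participant who starts dopaminergic therapy has no value. The SAP does not say so: censored change could be the last change before therapy or a model-based estimate.
- **That end-of-study belief is used to predict earlier improvement.** SAP 6.8.6 names no administration. The defect is that it is unspecified.
- **That the plan reads one association as cause in both directions.** Both sections speak only of predictors. The models also differ: placebo-arm responder status on Parts IB and II or Part III in one, belief of inosine assignment in the other.
- **That these models are the plan's check on blinding.** The main blinding evaluation is in SAP 4.7: proportions guessing correctly or incorrectly, and the odds ratio of a true against a wrong guess, by class of respondent. It is unaffected.

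**Conclusion.** The point holds for the week-6 item in SAP 6.8.7. Taken through its own cross-reference, the predictor spans baseline to week 12, and nominally 42 of those 84 days follow the guess. This rests on the scheduled visit days and on reading the reference to 6.6.8 literally. The 58% figure is illustrative and the conclusion does not depend on it. The neighbouring items, which keep to preceding events and exposure, suggest an oversight.

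The point on SAP 6.8.6 is narrower: neither the administration nor the respondent is named, so time order is not secured. Both models are exploratory items under SAP 6.8, so the stake is how a secondary finding about belief can be read. This is a minor correction.

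**What to change.** In SAP 6.8.7, define the symptom predictor of the V02 response as change in MDS-UPDRS I-III from baseline to V02, using scores obtained before any dopaminergic therapy, and remove the reference to 6.6.8 from that item. Parts I to III are already scheduled at V02 (Protocol 7.2.3). Leave the late item as it is.

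In SAP 6.8.6, for the belief predictor only, name the participant's week-6 answer and count improvement only at V03 or later. Keep the any-visit outcome for the eight baseline predictors, so that early placebo response is not discarded for their sake.

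The cost is SAP wording: no new data, visits or sample size. Under SAP 6.1.4 the SAP must be approved before the final data lock and unblinding, so the change should be made by then.
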